3.1 Primary Endpoint(s)

For US-specific protocol, the co-primary efficacy endpoints are

- The achievement of CDAI clinical remission at Week 12
- The achievement of endoscopic response at Week 12

For global protocol outside US, the co-primary efficacy endpoints are

- The achievement of clinical remission at Week 12
- The achievement of endoscopic response at Week 12

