3.3 Other Efficacy Endpoint(s)

The primary and secondary efficacy endpoints are listed in Section 3.1 and Section 3.2, respectively. The additional efficacy endpoints for each induction period are:

12-Week Induction Period:

- Change from baseline in IBDQ at Week 4, Week 12 respectively
- Change from baseline in individual IBDQ domain scores (bowel, emotional, social, systemic) at Week 4, Week 12 respectively

- The achievement of IBDQ remission (IBDQ \geq 170 points) at Week 4, Week 12 respectively
- The achievement of IBDQ response (increase in IBDQ \geq 16 points from baseline) at Week 4, Week 12 respectively
- Change from baseline in WPAI-CD at Week 4, Week 12 respectively
- Change from baseline in European Quality of Life 5 Dimensions (EQ-5D-5L) at Week 4, Week 12 respectively
- Change from baseline in FACIT-Fatigue total score and individual items at Week 4, Week 12 respectively
- The achievement of increase in FACIT-Fatigue total score from baseline \geq 7 at Week 12
- The achievement of increase in FACIT-Fatigue total score from baseline \geq 9 at Week 12
- The achievement of increase in FACIT-Fatigue total score from baseline \geq 11 at Week 12
- Change from baseline in Short Form-36 (PCS and Mental Component Summary score [MCS] and all 8 domain scores) at Week 4, Week 12 respectively
- Change from baseline in Fecal calprotectin (FCP) at Week 4, Week 12 respectively
- Change from baseline in high-sensitivity C-reactive protein (hs-CRP) at Week 4, Week 8, Week 12 respectively
- Change from baseline in average daily AP score at Week 4, Week 8, Week 12 respectively
- Change from baseline in average daily SF at Week 4, Week 8, Week 12 respectively
- The achievement of clinical remission at Week 4, Week 8, Week 12 respectively
- The achievement of enhanced clinical response at Week 4, Week 8, Week 12 respectively
- The achievement of clinical response at Week 4, Week 8, Week 12 respectively

- Change from baseline in SES-CD at Week 12
- The achievement of a SES-CD ulcerated surface subscore ≤ 1 at Week 12 in subjects with a SES-CD ulcerated surface subscore ≥ 2 at baseline
- Patient Global Impression of Severity (PGIS) response at Week 4, Week 8, Week 12 respectively
- The achievement of subjects who report symptoms to be "Minimal" or "Absent" on the PGIS at Week 4, Week 8, Week 12 respectively, for subjects who did not report symptoms to be "Minimal" or "Absent" at baseline

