added to all cells in the corresponding table in order to prevent dividing by 0, as suggested in Greenland and Robins (1985)³. Point estimates and 95% confidence interval (CI)s for the difference in proportions between each of risankizumab treatment groups and placebo will be provided. Construction of CI for the common risk difference will be based on the Mantel-Haenszel estimate adjusting for stratification factors. For binary endpoints with small number of sample size (such as achievement of no draining fistulas at Week 12 in subjects with draining fistulas at baseline), or small number of responders (such as occurrence of CD-related hospitalization through Week 12), Chi-square test (or Fisher's exact test if $\geq 20\%$ of the cells have expected cell count < 5) will be performed.

Analysis of Continuous Variables:

For continuous variables, the model based mean and standard error will be provided. The baseline and visit means will also be presented for each treatment group. Continuous variables collected longitudinally will be using a Mixed-Effect Model Repeated Measurement (MMRM) model. Continuous efficacy variables which are collected at only one post-baseline visit (such as SES-CD) will be analyzed using an Analysis of Covariance (ANCOVA) model. Point estimates and 95% CIs of mean change from baseline within treatment groups, and between each risankizumab treatment group and placebo will be provided. The baseline refers to the last non-missing observation before the first administration of any study drug or randomization if no study drug is given.

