 - Markov Chain Monte Carlo (MCMC) will be first applied to augment data into monotonic missing pattern, where applicable, and PROC MI will be used to generate 30 datasets using the regression method. If the binary endpoints are derived from the continuous variables, PROC MI will be applied to the continuous variables. The variables to be included in the imputation model are: treatment group, randomization stratification factors (Number of prior biologics failed (0, 1, > 1), baseline steroid use (Yes, No)), age, gender, weight and if applicable, baseline measurement and post-baseline measurements at each visit up to the end of the analysis period. The random seed for MCMC and the random seed for PROC MI are specified in [Appendix H](#). The imputed post-baseline measurements will be rounded to the same precision as the observed data before the determination of responder status. Prior to applying CMH model, subjects will be characterized as responders or non-responders based on MI imputed values if missing due to Covid-19, otherwise subjects will be considered as non-responder for missing due to other reasons in the NRI-C approach. Using the CMH model adjusted by randomization stratification factors, the endpoints will be analyzed using each of the 30 imputed datasets. SAS PROC MIANALYZE will be used to generate the final inferences of the risk difference between the risankizumab treatment group and placebo group, using Rubin's rule. The CD-related corticosteroid censoring rule, as specified in [Section 8.2.2](#) and [Appendix J](#), will be applied before and after applying MI for efficacy assessments.

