8.3.2 Continuous Endpoints

For continuous efficacy endpoints where Mixed-Effect Model Repeat Measurement (MMRM) analysis or Analysis of Covariance (ANCOVA) is performed, missing data will be handled using the following approaches.

- **Mixed-Effect Model Repeat Measurement (MMRM):** The repeat measurement analysis will be conducted using a mixed model including observed measurements at all post-baseline visits, after the CD-related corticosteroids censoring rule is applied (see Section 8.2.2 and Appendix J). The mixed model includes the categorical fixed effects of treatment, visit and treatment-by-visit interaction, stratification factors at randomization, and the continuous fixed covariates of baseline measurement. An unstructured variance covariance matrix will be used. Parameter estimation is based on the method of restrictive maximum likelihood (REML). MMRM will be the primary approach in the analysis of continuous variables.
- **ANCOVA-C:** For continuous efficacy variables that are collected at only one post-baseline visit (such as SES-CD), the missing data due to COVID-19 will be imputed using MI first before applying the ANCOVA model.

In addition, As Observed (AO) and Pattern Mixture Model (PMM) will be performed as sensitivity analysis, if appropriate, for categorical or continuous endpoints.

- **As Observed (AO):** The AO analysis will not impute values for missing evaluations, and thus a subject who does not have an evaluation on a scheduled visit will be excluded from the AO analysis for that visit. AO will include all values collected in the study regardless of censoring for steroids or not.

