8.4.2 Handling of Missing Data for the Primary Efficacy Endpoint(s)

The NRI-C approach for handling missing data will be used for primary analysis for the co-primary endpoints for the 12-Week Induction Period.

The NRI-NC and PMM approaches for handling missing data will be conducted as sensitivity analyses for the co-primary endpoints for the 12-Week Induction Period if applicable. For PMM approach, the pre-specified missing-data patterns are given as below. Other missing data patterns could be explored if deemed necessary.

| Missing-data Patterns |
|---|
| Non-completers (missing at Week 4 or at Week 8 or at Week 12) |
| Completers |

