Appendix H. Random Seeds

In case of non-convergence, the random seed will be updated by adding 100000 at each attempt until convergence of model happens.

Table H-1. Random Seeds for NRI-C

| Variables | Random Seed | |
|--------------------------------------|----------------|---------|
| | MCMC Procedure | PROC MI |
| CDAI | 50001 | 60001 |
| SES-CD (for 20 individual variables) | 50002 | 60002 |
| SF score | 50003 | 60003 |
| AP score | 50004 | 60004 |
| EIM | 50005 | 60005 |
| FACIT-Fatigue | 50006 | 60006 |
| IBDQ total score | 50009 | 60009 |
| PGIS | 50010 | 60010 |
| PGIC | 50011 | 60011 |

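### A Week 12 SES-CD wholly missing due to COVID-19 is imputed without using the subject's own on-treatment data; adding a few auxiliaries already collected is a cheap improvement

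*SAP*

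**What the plan says.** Both the US and the global plan have "The achievement of endoscopic response at Week 12" as a co-primary endpoint (SAP Section 3.1). Section 8.4.2 states: "The NRI-C approach for handling missing data will be used for primary analysis for the co-primary endpoints". Under NRI-C a subject with a missing evaluation counts as a non-responder, unless the cause is COVID-19 infection or a logistical restriction. In that case the value is multiply imputed.

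Section 8.3.1 lists the imputation model. It opens with "The variables to be included in the imputation model are: treatment group, randomization stratification factors" (number of prior biologics failed and baseline steroid use) and continues with "age, gender, weight and if applicable, baseline measurement and post-baseline measurements at each visit up to the end of the analysis period". It names no biomarker and no other instrument.

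Section 8.3.2 gives SES-CD as the example of "continuous efficacy variables that are collected at only one post-baseline visit (such as SES-CD"), and Section 8.1 says the same. Appendix H sets seeds variable by variable. SES-CD has its own entry, "SES-CD (for 20 individual variables"), separate from CDAI, SF and AP. Fecal calprotectin (FCP) and hs-CRP have no entry.

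Section 3.3 shows what is collected on treatment. One item is "Change from baseline in Fecal calprotectin (FCP) at Week 4, Week 12 respectively". hs-CRP and average daily SF and AP are assessed at Weeks 4, 8 and 12.

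**The concern.** For CDAI, SF and AP, a Week 12 value missing due to COVID-19 can be imputed from the same measure at Weeks 4 and 8. For SES-CD there is no earlier on-treatment value. When the Week 12 endoscopy is wholly missing, the post-baseline term in the list adds nothing, and the imputed value reflects the average for the subject's arm and baseline profile, not how that subject did.

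Section 8.3 justifies imputation by assuming that COVID-19 missingness is unrelated to unobserved values, and calls this missing at random (MAR). MAR still lets missingness depend on observed values, including on-treatment symptoms and markers. If it does, those values must be in the imputation model for the imputation to be unbiased. At stake is the accuracy of the endoscopic co-primary estimate. The same imputed SES-CD also feeds endoscopic remission, ulcer-free endoscopy and the composites with endoscopic response in Section 3.2.

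**Working it through.** **Inputs from the SAP (Section 2.4).** Endoscopic response 25.5% on risankizumab and 8% on placebo, a difference of 17.5 points; 342 versus 171 subjects; Fisher's exact test at two-sided 0.025; stated power 99%. (Section 2.2 attaches 342 to placebo and 171 to the 1200 mg group; the Section 2.4 sizes are used because they carry the power statement.)

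**Reproducing the stated power.** Enumerating both binomials gives an exact Fisher power of 99.8%, and the normal approximation also gives 99.8%. The stated 99% is reproduced and is not in dispute.

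**Inputs that are assumptions.** The SAP gives no COVID-19 missing fraction and no correlation between on-treatment markers and endoscopic change. Ranges are used for both.

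**How the bias arises.** With fraction f missing in an arm:

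bias in arm rate = f × (imputed response rate − true response rate among the missing)

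bias in difference = risankizumab bias − placebo bias

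**Simulation A: subjects doing worse miss the endoscopy more often.** Latent-normal SES-CD improvement, 342 versus 171, 30 imputations with Rubin's rules, 300 replicates per setting, log-odds of a missed endoscopy 0.8 per SD of the marker. The model with treatment and baseline is compared with the same model plus one on-treatment marker. Values are mean differences in percentage points.

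| Nominal missing | Marker correlation | Complete data | SAP-type model | With marker | SAP-type − complete |
|---|---|---|---|---|---|
| 2% | 0.3 | 17.59 | 17.68 | 17.59 | +0.09 |
| 2% | 0.5 | 17.55 | 17.67 | 17.51 | +0.12 |
| 2% | 0.7 | 17.65 | 17.88 | 17.65 | +0.23 |
| 5% | 0.3 | 17.63 | 17.92 | 17.68 | +0.29 |
| 5% | 0.5 | 17.46 | 17.96 | 17.54 | +0.50 |
| 5% | 0.7 | 17.10 | 17.61 | 17.10 | +0.51 |
| 10% | 0.3 | 17.66 | 17.98 | 17.56 | +0.32 |
| 10% | 0.5 | 17.11 | 17.81 | 17.07 | +0.70 |
| 10% | 0.7 | 17.58 | 18.60 | 17.60 | +1.02 |

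The difference is overstated by 0.1 to 0.2 points at 2% and 0.3 to 1.0 at 10%. With the marker added, the estimate is within about 0.1 point of complete data throughout. The missing rates are those at average marker value. Averaging 1/(1 + exp(−(logit 0.10 + 0.8z))) over a standard normal z gives about 12%, so the nominal 10% row is slightly generous.

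**Simulation B: subjects doing better miss the endoscopy more often.** 1,000,000 per scenario, 10-12% missing, correlation 0.3 to 0.5, odds ratio 1.5 to 2 per SD. At the upper end the true response among the missing is 36% and 13%, while the model without the marker imputes about 24% and 7%:

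- risankizumab: 0.12 × (24 − 36) = −1.4 points
- placebo: 0.12 × (7 − 13) = −0.7 points
- difference: −1.4 − (−0.7) = −0.7 points

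Across scenarios the difference is understated by about 0.3 to 0.7 points. The sign is opposite to simulation A and the size is similar.

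**Missingness unrelated to response.** In simulation A with random missingness, the SAP-type estimate is within 0.1 point of complete data in all nine settings. The largest precision gain from the marker is a standard error of 0.0323 instead of 0.0328 (10% missing, correlation 0.7), which is 0.0005/0.0328 = 1.5%.

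**Power.** At least 99.7% with either imputation model in every setting of simulation A.

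**The case against.** The SAP's reasons for COVID-19 missingness are external: quarantine, travel limits, strained healthcare resources. If they operate independently of the subject's condition, leaving out the markers causes no bias. An endoscopy missed for any other reason is a non-response and is never imputed. This stands, and it makes the bias conditional. It does not close the point, because the assumption invoked is MAR, which is weaker than missing completely at random.

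The size is small. Even 1.0 point compares with an assumed difference of 17.5 points and a standard error of about 3.1 points. NRI-NC removes the imputation altogether: with all 10% or 12% set to non-response, power is still 99.5% or 99.4%. This also stands. NRI-NC shows whether the conclusion hangs on the imputation. However, neither it, the as-observed analysis nor the pattern-mixture model uses the markers to improve the estimate.

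The text leaves some room. SES-CD is imputed as 20 items, so a partly scored endoscopy may contribute if the items are imputed jointly. Nor does Section 8.3.1 expressly confine the measurements to the same instrument; that is inferred from its wording and the separate seeds. The point is therefore exact only for a wholly missing endoscopy, and if other instruments were meant, the SAP should say so.

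Finally, the simulations use one latent variable and one marker, not 20 ordinal items. If the whole Week 12 visit is missed, Week 12 FCP and hs-CRP may be missing too, so the benefit may be nearer the lower end of the range.

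**Conclusion.** The gap is real but modest. For a Week 12 endoscopy wholly missing due to COVID-19, the listed model uses treatment group, strata, age, gender, weight and baseline SES-CD, and nothing about the subject's own on-treatment course.

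A reader might infer that the endoscopic co-primary is biased, or biased in a known direction. The SAP does not support that. Bias arises only if missingness tracks on-treatment disease activity, and its sign follows the mechanism: overstated if subjects doing worse miss the endoscopy, understated if subjects doing better do. Under the assumed ranges it is roughly 0.1 to 0.2 points at 2-3% missing and 0.3 to 1.0 at 10%. Under purely logistical missingness it is nil.

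A reader might also infer that imputation ignores treatment. It does not: randomised group is in the model, so the arm's average response is carried through. Nor is the success of the trial at risk, since power is essentially unchanged. What can be gained is a more credible MAR assumption and a slightly more precise estimate.

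**What to change.** In Section 8.3.1, name a small set of on-treatment auxiliaries for the SES-CD imputation model: for example the Week 4 and latest available values of log FCP, log hs-CRP, average daily SF and average daily AP. State that they are imputed jointly in the MCMC step when missing, and that the corticosteroid censoring applies as already planned. If other instruments were already meant to be included, say so explicitly.

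The cost is a sentence or two and some extra variables in PROC MI. The downside is a larger model alongside the 20 SES-CD items. Keep the set small and prespecify a fallback to fewer auxiliaries if the model does not converge; Appendix H currently provides only for changing the seed. If the primary model is to stay as it is, run the auxiliary version as a sensitivity analysis or give the reason for leaving the markers out.

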3.0 Endpoints

Below are the definitions of the endpoints used in the efficacy analysis:

- **Clinical remission:** average daily SF ≤ 2.8 and not worse than baseline AND average daily AP score ≤ 1 and not worse than baseline
- **Enhanced clinical response:** $\geq 60\%$ decrease in average daily SF and/or $\geq 35\%$ decrease in average daily AP score and both not worse than baseline, and/or clinical remission
- **Clinical response:** $\geq 30\%$ decrease in average daily SF and/or $\geq 30\%$ decrease in average daily AP score and both not worse than baseline
- **Endoscopic response:** decrease in SES-CD $> 50\%$ from baseline (or for subjects with isolated ileal disease and a baseline SES-CD of 4, at least a 2 point reduction from baseline), as scored by central reviewer

- **Ulcer-free endoscopy:** SES-CD ulcerated surface subscore of 0 in subjects with SES-CD ulcerated surface subscore ≥ 1 at baseline, as scored by a central reviewer
- **Endoscopic remission:** SES-CD ≤ 4 and at least a 2 point reduction versus baseline and no subscore greater than 1 in any individual variable, as scored by a central reviewer
- **CDAI clinical response:** reduction of CDAI ≥ 100 points from baseline
- **CDAI clinical remission:** CDAI < 150
- **SF remission:** average daily SF ≤ 2.8 and not worse than baseline
- **AP remission:** average daily AP score ≤ 1 and not worse than baseline

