8.3.1 Categorical Endpoints

For binary efficacy endpoints, missing data will be handled using the following approaches:

- The primary approach for handling missing data in the analysis of binary endpoints will use **Non-Responder Imputation (NRI) while incorporating Multiple Imputation (MI) to handle missing data due to **CCOVID-19 (NRI-C)**.
 - The NRI-C will categorize any subject who does not have an evaluation during a pre-specified visit window (either due to missing assessment or due to early withdrawal from the study) as a non-responder for the visit. The only exception is that missing data due to COVID-19 infection or logistical restriction will be handled by MI. At each visit, subjects will be characterized as responders or non-responders based on MI imputed values if missing due to Covid-19, otherwise subjects will be considered as non-responder for missing due to other reasons in the NRI-C approach. Of note, subjects will be counted as non-responders thereafter and will not be imputed by MI after the CD-related corticosteroids censoring time point as specified in Section 8.2.2 and [Appendix J](#).**
- A sensitivity analysis for binary endpoints will use **NR**I with **No** special data handling for missing due to **CCOVID-19 (NRI-NC)**.

- NRI-NC will be performed in the same way as NRI-C without the exception above. Missing due to COVID-19 infection or logistical restriction will also be counted as non-responders. This is the same method as "NRI" as defined in the protocol.
- Details on MI method are described below:

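### Stool frequency and abdominal pain appear to be imputed in separate runs although clinical remission needs both; the SAP should specify joint imputation (small effect, low severity)

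*SAP*

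**What the plan says.** Section 3.0 defines clinical remission as "average daily SF ≤ 2.8 and not worse than baseline AND average daily AP score ≤ 1 and not worse than baseline", so both components must be met. Section 3.1 makes it one of two co-primary endpoints outside the US ("For global protocol outside US, the co-primary efficacy endpoints are" clinical remission and endoscopic response). Section 3.2 ranks it first among the US secondary endpoints; the US clinical co-primary is CDAI remission.

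The primary missing-data method for the co-primary endpoints is NRI-C (Section 8.4.2). Missing subjects count as non-responders, and "The only exception is that missing data due to COVID-19 infection or logistical restriction will be handled by MI" (Section 8.3.1).

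On the imputation itself, Section 8.3.1 says "If the binary endpoints are derived from the continuous variables, PROC MI will be applied to the continuous variables". It then lists the model variables: treatment group, two stratification factors, age, gender, weight and, if applicable, "baseline measurement and post-baseline measurements at each visit up to the end of the analysis period". It does not say whether the SF model contains AP, or the reverse.

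Appendix H, Table H-1, has one row for each imputed measure. Two of them read "SF score | 50003 | 60003" and "AP score | 50004 | 60004". In the same table a multi-variable run is marked as such: "SES-CD (for 20 individual variables) | 50002 | 60002".

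**The concern.** If SF and AP at Week 12 are drawn in two unconnected runs, each draw depends only on that measure's own history. Whatever correlation remains between the two at Week 12 is lost. For an endpoint that needs both criteria, independent draws understate the chance of meeting both whenever that remaining correlation is positive. Positive correlation is plausible: both are symptoms of the same disease, and both are diary items in the CDAI (Appendix D).

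This matters because NRI-C is the primary analysis, and Section 8.3 gives its purpose as reliable treatment-effect estimates as if the pandemic had not intervened. Under separate runs the subjects whom MI is meant to serve get a biased remission rate even if the missing-at-random assumption is true.

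The same gap reaches the ranked endpoints that join a clinical response with endoscopic response (US secondary 6, global secondary 7), because CDAI, SF, AP and SES-CD each have their own row in Table H-1.

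**Working it through.** **Inputs from the SAP (Section 2.4).** Clinical remission 27.8% against 12%; 342 against 171 subjects; Fisher's exact test at two-sided 0.025; stated power 97%.

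**Inputs not in the SAP, assumed.** SF-AP correlation r from 0.2 to 0.6; correlation ρ between any two visits within a measure from 0.4 to 0.75; share missing due to COVID-19 from 1% to 10%; baseline, Week 4 and Week 8 observed, Week 12 missing. SF and AP are treated as standard normal with a common cut-off c, and the condition on worsening from baseline is left out for simplicity.

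**Step 1, the plan's own figure.** Exact enumeration of the Fisher test gives 97.7%, consistent with the stated 97%.

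**Step 2, what separate runs do.** With equal correlation ρ across visits, three earlier visits explain a share R² = 3ρ²/(1 + 2ρ) of Week 12 variance: 0.267, 0.491 and 0.675 for ρ = 0.4, 0.6 and 0.75. The true Week 12 correlation is r. With residuals drawn independently, the imputed pair has correlation r × R² only. With Φ₂ the bivariate normal distribution function:

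- true rate: Φ₂(c, c; r), which fixes c;
- imputed rate under separate runs: Φ₂(c, c; r × R²).

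Example, r = 0.4 and ρ = 0.4: c = -0.097 gives the true 27.8%. The imputed correlation is 0.4 × 0.267 = 0.107, and the imputed rate is 23.0%. For placebo c = -0.616, and 12% becomes 8.4%.

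| r | ρ | Imputed, true 27.8% | Imputed, true 12% | Difference (true 15.8 points) |
|---|---|---|---|---|
| 0.2 | 0.4 | 25.4% | 10.1% | 15.3 |
| 0.2 | 0.6 | 26.2% | 10.7% | 15.5 |
| 0.2 | 0.75 | 26.8% | 11.2% | 15.6 |
| 0.4 | 0.4 | 23.0% | 8.4% | 14.6 |
| 0.4 | 0.6 | 24.4% | 9.5% | 15.0 |
| 0.4 | 0.75 | 25.6% | 10.4% | 15.3 |
| 0.6 | 0.4 | 20.3% | 6.8% | 13.5 |
| 0.6 | 0.6 | 22.5% | 8.2% | 14.2 |
| 0.6 | 0.75 | 24.3% | 9.5% | 14.8 |

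A simulation of 2,000,000 subjects at ρ = 0.4 and 0.6 agrees to within about 0.1 points. In it, joint imputation returned 27.7-27.9% and 12.0% in every scenario. At r = 0 there is no bias. At r = -0.2 (ρ = 0.6) it reverses: 29.4% is imputed for a true 27.8%.

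**Step 3, effect over the full arms.** Loss in the treatment difference = share missing × (15.8 - difference among imputed subjects).

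- r = 0.4, ρ = 0.4, 10% missing: 0.10 × (15.8 - 14.57) = 0.12 points.
- Worst case run, r = 0.6, ρ = 0.4, 10% missing: 0.10 × (15.8 - 13.54) = 0.23 points.
- Mild case, r = 0.2, ρ = 0.6, 1% missing: 0.003 points.

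The standard error of the difference is √(0.278 × 0.722/342 + 0.12 × 0.88/171) = 3.5 points, so the worst case is about 0.23/3.5 = 7% of one standard error. Fisher power recomputed at the shifted rates stays at 97.7%.

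**Step 4, other composites.** Enhanced clinical response (Section 3.0) joins its SF and AP decreases by and/or, requires that neither measure worsens, and also admits remission. Since P(A or B) = P(A) + P(B) - P(A and B), independent draws raise the either-or part and lower the both-required parts. A simulation with assumed means and SDs (r 0.2-0.6, ρ 0.4-0.75) moved the active-type rate among imputed subjects by -0.1 to +2.1 points and the placebo-type rate by -1.2 to -3.0, so the difference widened. For the combined clinical-plus-endoscopic endpoints no size was computed; it depends on a correlation with SES-CD that the SAP does not give.

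**The case against.** The strongest reply is that the premise is inferred. A reader might take Table H-1 to say that SF and AP are imputed separately, but no sentence says so. A seed pair does not define a model's covariates, and an SF run could carry AP. That stands, and the point is worded accordingly. It does not remove the point: the variable list names no second outcome, and the table marks the one run that covers many variables. If a joint model was intended, the text does not specify it, and two programmers could produce different primary results.

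A second reply is that the effect is negligible and, for clinical remission with positive correlation, conservative. This also stands and sets the severity.

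A third is that the case where only one of SF and AP is missing will be rare, since both come from the same diary, and that diary data may survive a cancelled visit, so 10% missing may be high. Both are fair; the argument here uses the case where both are missing, and the missing share is an assumption.

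A fourth is that NRI-NC (Section 8.4.2) and as-observed analyses (Section 8.4.4) are already planned. They would show whether conclusions depend on the imputation, but they do not repair it. NRI-NC counts the same subjects as non-responders (at 10% missing the difference is 0.90 × 15.8 = 14.2 points), and the as-observed analysis also changes the corticosteroid handling (Section 8.3.2).

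**Conclusion.** The point holds as a low-severity specification gap. As written, Section 8.3.1 and Table H-1 imply independent imputation of two components that clinical remission requires together. If they stay positively correlated given their own histories, imputed remission among COVID-19-missing subjects is too low: at an assumed correlation of 0.4, about 23-26% for a true 27.8% and 8-10% for a true 12%. With an assumed 1-10% missing, the full-arm difference falls by at most about 0.2 points and power is unchanged.

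Four stronger readings are not supported:

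- That remission rates are too low without condition: the bias vanishes at zero residual correlation and reverses if it is negative, and the SAP gives no value.
- That the primary conclusion is at risk: the shift is a small fraction of one standard error.
- That the US co-primary endpoints are affected: CDAI is imputed as a total and SES-CD in its own run, so the co-primary effect is confined to the plan outside the US.
- That enhanced clinical response is biased downward: its and/or definition leaves the direction open, and the treatment difference may widen.

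**What to change.** In Section 8.3.1, state that SF and AP are imputed together in one model containing both measures at baseline and Weeks 4, 8 and 12. Imputing each with the other as a covariate is acceptable if the covariate includes the other's Week 12 value, imputed first in the same dataset where it is missing. Adding only its earlier visits would leave the residual correlation out.

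For the endpoints that combine clinical and endoscopic response, include the clinical measure when imputing SES-CD, where that model converges. Derive every composite from the same imputed dataset. Merge or relabel the SF and AP rows of Table H-1 to match.

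The cost is a sentence or two and a table edit, with no new data. It should be settled before the 12-Week Induction Period is unblinded, because afterwards it would be a post-hoc choice within the primary analysis.
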